BCG, a vaccine given to over 120 million infants annually to protect against TB, represents a potential prophylactic intervention for the prevention of COVID-19. In addition to protecting against TB, BCG has beneficial off target (also termed 'heterologous' or 'non-specific') effects that protect against unrelated infections in children and adults.

The beneficial off-target effects of BCG vaccination have been most extensively studied in children. A world health organisation (WHO)-commissioned meta-analysis of 12 studies in high mortality settings concluded that BCG vaccination reduces all-cause mortality in children under 5-years of age by 30-53%. This protection is evident within days of vaccination is proposed to be attributable to reduced deaths from infections other than TB, particularly respiratory tract infections and sepsis. Two large cohort studies in children similarly found that BCG reduces non-TB infections. The first, a 25-year retrospective study of over 150,000 children from 33 countries reported that BCG-vaccinated children had an up to 37% lower risk of acute lower respiratory tract infections. The second, a study of paediatric hospitalisations in Spain, found that BCG-vaccinated children had a 41% lower risk of serious respiratory infection and 53% lower risk of sepsis not related to TB.

In adults, in a human challenge model, prior BCG vaccination reduced viraemia by over 70% and improved anti-viral immune responses to yellow fever vaccine virus. Notably, yellow fever virus is a single-stranded, positive-sense RNA virus like SARS-CoV-2. Consistent with BCG mediated protection against infections, in two randomised control trials in adults, BCG vaccination reduced incidence of acute upper tract respiratory infections by 70-80%. Several studies have also shown that BCG can reduce symptoms in human papilloma virus infection and herpes simplex virus infection adults.

A plethora of studies in animal models, have also shown that BCG protects against disease and mortality caused by a wide range of bacterial, fungal, protozoan and viral infections including infections with single-stranded, positive-sense RNA viruses.

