## 3 TRIAL OBJECTIVES AND OUTCOMES

## 3.1 Objectives

Two primary outcomes have been chosen for this study: occurrence of symptomatic COVID-19 and occurrence of severe COVID-19. Considering the number of unknown factors and the little knowledge of this new virus, we deemed it of clinical importance to have sufficient power to detect the potential effect of BCG vaccine compared to control for both outcomes (occurrence of symptomatic COVID-19, as well as occurrence of severe COVID-19). Our hypothesis is that, compared to control, the BCG vaccine will reduce both the number of cases of COVID-19 (increase the number of asymptomatic SARS-CoV-2 infections) and the number of severe cases of COVID-19. In other words, we have the hypothesis that BCG vaccine would be able to shift the "severity of COVID-19" curve down, i.e. to generally reduce the severity of the symptoms in healthcare workers. Because of the potential for multiplicity testing, the method of controlling type I error is explained in the sample size section (11.1).

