5. To determine if BCG vaccination (Intervention) compared with placebo (Comparator) prolongs the time to first COVID-19 episode (Outcome) measured over 6 and 12 months following randomisation (Time) in healthcare workers (Participants).	Time to first symptom of COVID-19 over the 6 and 12 months following randomisation.
6. To determine if BCG vaccination (Intervention) compared with placebo (Comparator) reduces the severity of COVID-19 (Outcome) measured over 6 and 12 months following randomisation (Time) in healthcare workers (Participants).	All the following measures will be assessed, over the 6 and 12 months following randomisation.  Number of episodes of COVID-19 disease as (defined above)  Asymptomatic SARS-CoV-2 infection (defined as:

Study Name: BCG vaccination to Reduce the impact of COVID-19 in healthcare workers (BRACE) trial

RCH HREC number: 62586

Version & date: version 12.0 dated 17May2022

0	Evidence of SARS-CoV-2 infection (by	
seroconversion) and		

- o Absence of any episodes of illness (using selfreported questionnaire) and
- o No evidence of exposure prior to randomisation
- Number of days unable to work (using self-reported questionnaire) due to COVID-19 as defined above (excludes quarantine/workplace restrictions)
- Number of days confined to bed (using self-reported questionnaire) due to COVID-19 as defined above
- Number of days with symptoms due to for COVID-19
- Pneumonia cases (using self-reported questionnaire and/or medical/hospital records) due to COVID-19.
- Need for oxygen therapy (using self-reported questionnaire and/or medical/hospital records) due to COVID-19
- Admission to critical care and duration of stay (using self-reported questionnaire and/or medical/hospital records) due to COVID-19.
- Need of mechanical ventilation and duration (using self-reported questionnaire and/or medical/hospital records)
- Hospitalisation and duration due to COVID-19 (using self-reported questionnaire and/or medical/hospital records)
- Death due to COVID 19

7. To determine if BCG vaccination (Intervention) compared with placebo (Comparator) reduces the rate and severity of illness (fever or at least one sign or symptom of respiratory disease) measured over the 12 months following randomisation (Time) in healthcare workers (Participants).

All the following measures will be assessed, over the 12 months following randomisation

For the following outcomes, fever or respiratory illness will be defined as:

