#### Questionnaires

#### Baseline

- Comorbidities: diabetes, cardiovascular disease, chronic respiratory disease, hypertension
- Risk factors: smoking, body mass index (calculated with weight and height)
- BCG/TB history: Prior BCG vaccination, ever positive TST
- Influenza immunisation: date of last influenza vaccine (if within influenza season)
- Exposure (presence of COVID-19 cases at workplace, average days working in hospital or other healthcare settings as appropriate)
- Other: Recurrent herpes infection (such as cold sores)

Regular (generally weekly) questionnaires on smartphone app, via phone call or via electronic messages

 Any symptoms of COVID-19: fever or at least one sign or symptom of respiratory disease such as sore throat, cough, shortness of breath, respiratory distress/failure (y/n)

For each episode of illness (via smartphone app, via phone call or via electronic messages)

- Which symptoms of COVID-19: fever, cough, shortness of breath and/or difficulty breathing, runny/blocked nose, sore throat, fatigue, muscle and/or joint ache, headache, nausea, vomiting and/or diarrhoea, loss of taste and smell
- Has a COVID-19 swab been taken? (if so what was the result)
- Date of/days since onset and cessation of symptoms
- Days absent from work (total number and number due to illness)
- ED presentations
- Hospital admission (oxygen, ICU admission, mechanical ventilation)
- Known test results
- If a swab has been taken for clinical purposes, who ordered it
- Impact on daily activities
- Days in bed
- Chest x-ray results

For local reaction to injection: the Vaccine Diary (daily diary for the two weeks following injection)

 Questionnaire collecting common reactions to the injection, including photograph of injection site

Periodic questionnaires (once every 3 months)

- Exposure (presence of COVID-19 cases at workplace, average days working in hospital or other healthcare settings as appropriate)
- Cold sore recurrence
- Request for participants to confirm the main episodes of illness experienced in the prior 3 months.
- Screening, exposure or treatment of TB

- Detail on other vaccinations
- Hospitalisation (any)
- Information regarding participation in any other COVID-19 preventative intervention clinical trials
- Injection site evolution and side effects (photo of injection site)
- Treatment that could influence COVID-19 outcome

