#### **Blood samples**

- At randomisation, a blood sample will be taken for later assessment of seroconversion (production of specific anti-SARS-CoV-2 antibodies). This will identify participants who had SARS-CoV-2 exposure and immunity prior to commencement of the study.
  - The baseline blood samples will be analysed in batch months after randomisation, so there will be no clinically actionable results. We will provide individualised results to participants via email after completion of the trial.
     This email will be sent to the applicable HRECs to review before being sent out to any participant.
  - o In Brazil, IGRA testing will be completed on pre-randomisation and 12-month blood samples as outlined in appendix 4.
- At 3 months and 6 months (+ 42 days) post randomisation, the study team will
  coordinate to collect study blood samples from participants and in a subset of
  participants at 9 and 12 months (+ 42 days) post randomisation. This will identify

- participants who had an immune response to SARS-CoV-2 (surrogate marker of infection) during the study. This is needed to determine asymptomatic SARS-CoV-2 infections.
- Blood samples will also be taken for assessment of the immune system. This will be
  used to meet the planned exploratory analyses related to vaccine induced changes in
  the immune system. These blood samples will be taken at the same time as blood
  collection for serum or plasma samples (i.e. at randomisation and post
  randomisation)
- In the eventuality that it is unfeasible to collect swab samples to confirm SARS-CoV-2 infection at the time of febrile or respiratory illness episodes (or conduct a validated RAT test), seroconversion may be used to associate episodes of febrile or respiratory illness with SARS-CoV-2 infection. Therefore, for episodes of febrile or respiratory illness where a swab sample cannot be taken, 1 month after the onset of symptoms (expected peak post-infection antibody production), participants may be asked to come to the hospital to provide a blood sample. If rapid point-of care testing is available, these tests may be distributed to participants to self-test. Should these alternative methods of testing become required, an amendment will be submitted to HRECs to outline the process and submit any information for participants. This testing will not be conducted without further consultation with and approval from the HRECs, including providing the HRECs with details of the test and its efficacy.

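### Asymptomatic SARS-CoV-2 infection requires no illness at any time in the 6 or 12 months, so an unrelated illness far from the infection removes a true case, and does so unequally if BCG lowers such illness

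*Protocol*

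**What the plan says.** Under objective 6, Protocol section 3.2 lists about a dozen measures of COVID-19 severity and introduces them with "All the following measures will be assessed, over the 6 and 12 months following randomisation". One is asymptomatic SARS-CoV-2 infection. It has three conditions, all required: seroconversion, "Absence of any episodes of illness" on the self-reported questionnaire, and no evidence of exposure before randomisation. The illness condition names no cause and no period of its own, so it takes the 6- and 12-month windows of the lead-in. Most neighbouring measures (days unable to work, days in bed, pneumonia, oxygen, critical care, death) are tied to COVID-19 as the cause.

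Section 7.3 describes the data:
- The regular questionnaire asks about "fever or at least one sign or symptom of respiratory disease such as sore throat, cough, shortness of breath". Each reported episode then yields symptoms, onset and cessation dates, and swab results.
- Blood is taken at baseline and "At 3 months and 6 months (+ 42 days) post randomisation", and only in a subset at 9 and 12 months. Of the follow-up bloods the Protocol says "This is needed to determine asymptomatic SARS-CoV-2 infections".

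On what BCG is expected to do, section 3.1 hypothesises that it will "increase the number of asymptomatic SARS-CoV-2 infections". Section 2.2 reports that in two adult trials "BCG vaccination reduced incidence of acute upper tract respiratory infections by 70-80" per cent. Section 2.3.1 cites a revaccination trial with upper respiratory infection in 2.1% on BCG and 7.9% on placebo. Objective 7 tests whether BCG reduces febrile or respiratory illness in general.

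**The concern.** Whether an infection was silent depends on what happened around the time of that infection. The definition makes it depend on the participant's whole illness history over 6 or 12 months. This has two consequences.

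- True asymptomatic infections are lost in both arms whenever the participant has an unrelated cold at another time. Because the window lengthens, a count that should only accumulate can fall between 6 and 12 months.
- Case status depends on non-COVID illness, which the trial hypothesises BCG will reduce. If BCG does so, fewer silent infections are discarded in the BCG arm, and the arm comparison moves in the direction that section 3.1 hypothesises without any effect on SARS-CoV-2. A biological effect is not needed: illness is self-reported, and sections 4.1 and 6.1 accept that participants cannot be fully blinded, so lower reporting in the BCG arm would act the same way.

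**Working it through.** The Protocol gives no expected figure for this outcome, so there is none to reproduce.

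**Step 1: apply the definition to three participants, all negative at baseline.**
- A: positive at month 3 without symptoms; PCR-negative cold in month 5. Not counted, although the infection preceded the cold.
- B: swab-negative sore throat in month 1; serology still negative at month 3; silent seroconversion by month 6. Not counted, although the sore throat preceded the negative blood sample.
- C: silent seroconversion by month 3; well to month 6; cold in month 9. Counted at 6 months, not at 12.

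The order of events alone settles A and C. In B, the negative sample about two months after the sore throat does so.

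**Step 2: formula.** Let the true risk of asymptomatic infection be equal in both arms, and unrelated illness be independent of infection. Let p be the control-arm risk of at least one unrelated febrile or respiratory illness in the window, and r the BCG risk ratio for it. The definition keeps a share 1-p of true cases in controls and 1-pr in the BCG arm. The false ratio, BCG to control, is (1-pr)/(1-p).

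**Step 3: numbers.** The only rates in the Protocol are those in section 2.3.1: p = 0.079 and pr = 0.021, so r = 0.021/0.079 = 0.27. Larger p are assumptions; r = 0.7 is an assumed weaker effect.

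| p | r | Control cases lost | False ratio |
|---|---|---|---|
| 0.079 (cited) | 0.27 (cited) | 7.9% | 0.979/0.921 = 1.06 |
| 0.3 (assumed) | 0.7 | 30% | 0.79/0.70 = 1.13 |
| 0.3 (assumed) | 0.27 | 30% | 0.919/0.70 = 1.31 |
| 0.5 (assumed) | 0.7 | 50% | 0.65/0.50 = 1.30 |
| 0.5 (assumed) | 0.27 | 50% | 0.865/0.50 = 1.73 |

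With r = 1 the false ratio is 1 at every p; cases are still lost, but equally.

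**Step 4: effect of the longer window.** At a constant illness rate with p = 0.5 at 6 months, the 12-month risk is 1 - 0.5² = 0.75. Of true silent infections in months 0 to 6, 50% are counted at 6 months and 25% at 12, so half of those already counted drop out. With p = 0.4 at 6 months and a rate ratio of 0.5 for BCG, the false ratio is 0.6^0.5/0.6 = 1.29 at 6 months and 0.36^0.5/0.36 = 1.67 at 12.

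**Step 5: effect of a time link.** Take a 3-month serology interval plus a 1-month allowance for antibody delay, so a 4-month window. With p = 0.5 at 6 months, 0.5^(4/6) = 63% of true cases are kept, before swab-negative episodes are disregarded. In the p = 0.4 example the false ratio becomes 0.6^(-0.5 × 4/6) = 1.19, and it no longer grows to 1.67 at 12 months. Disregarding swab-negative episodes reduces it further.

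**The case against.** The case for leaving the definition alone has four parts.

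- **Stakes.** This is one of many secondary measures, with no alpha or sample size attached. Unrelated illness by arm is reported under objective 7, so a reader could see whether it differed. That holds and limits the importance of the point. It does not repair the count.
- **Analysis plan.** Section 11.3 leaves the full details of each variable to a statistical analysis plan, which may link episodes to serology intervals. But section 3.2 itself states the conditions, and nothing elsewhere in the Protocol narrows them.
- **Specificity.** Seroconversion dates infection only to an interval of about three months with a 42-day window, swabs may be unavailable, and self-report is imperfect. A strict rule avoids calling a missed COVID-19 illness asymptomatic. That is a reason to exclude illness that could belong to the infection, not illness months away from it.
- **A naive time link would go wrong.** Section 7.3 expects peak antibody about one month after symptom onset, so a COVID-19 illness just before a negative sample could be missed. Section 3.2 also defines symptomatic COVID-19 by positive serology plus a symptom, with no stated time link, so changing objective 6 alone could put the same infection in both categories. Both objections stand, and the fix must meet them.

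A reader might infer that the outcome is heavily under-counted, or that the false ratio exceeds 2. The documents do not support either: p is not given, and the only cited rates imply about 8% of control cases lost and a ratio of 1.06. A reader might also infer that any BCG effect on other illness appears as more asymptomatic infection. That follows only if BCG lowers illness or its reporting. With no effect there is no differential bias, and with an increase the sign reverses. Finally, the wording covers illness of every kind, but the regular survey asks about fever and respiratory symptoms, so in practice the condition probably means a febrile or respiratory episode. A cold with cough or sore throat counts either way.

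**Conclusion.** The point holds for this secondary measure. As written, the definition discards true asymptomatic infections because of illness clearly separate in time, and lets a case counted at 6 months disappear at 12. Both follow from the wording alone.

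The bias between arms is conditional: it needs BCG to reduce unrelated illness or its reporting. The false ratio is then about 1.06 at the cited 7.9% against 2.1%, and about 1.1 to 1.7 for assumed p of 0.3 to 0.5 with r of 0.7 to 0.27. These figures assume that illness is independent of infection and that BCG has no effect on SARS-CoV-2. The cited rates come from a trial in adolescents, not healthcare workers, so the actual p could differ in either direction. The definition should be changed, because its error, if BCG works on other illness as hoped, would be read as support for the hypothesis in section 3.1.

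**What to change.** In section 3.2, objective 6, replace the illness condition with: *no episode of fever or respiratory illness with onset from a pre-specified antibody-delay allowance (for example about 1 month, in line with section 7.3) before the last negative sample up to the first positive sample, disregarding episodes with a negative SARS-CoV-2 PCR.* In addition:

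- Carry a 6-month case forward to 12 months regardless of later unrelated illness.
- Apply the same time link to serology-based symptomatic COVID-19 in section 3.2, so that one infection cannot be both symptomatic and asymptomatic.
- For infections after month 6, use the subset with 9- and 12-month serology, and say so.
- Keep the current rule of no illness at all as a sensitivity analysis.

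The cost is a few sentences in section 3.2 and changes to two outcome derivations. Illness dates, swab results and serology are already collected, except that serology after month 6 exists only in the subset. Since the wording of a primary outcome is touched, the change should be made before allocation is unblinded. Some COVID-19 episodes with a false-negative swab may be classed as asymptomatic, and untested unrelated illness inside the window still excludes some cases, so the bias is reduced rather than removed. The retained strict version would show how much the choice matters.

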## Оитсомея Primary outcomes: 1. Symptomatic COVID-19 defined as: AND OUTCOME **MEASURES** a positive SARS-CoV-2 test (PCR, RAT or serology) over the 6 months following randomisation PLUS • fever (using self-reported questionnaire)OR • at least one sign or symptom of respiratory disease, including cough, sore throat, shortness of breath, respiratory distress/failure (using self-reported questionnaire) 2. Severe COVID-19 defined as: a positive SARS-CoV-2 test (PCR, RAT or serology) over the 6 months following randomisation PLUS • Death (as a consequence of COVID-19) • Hospitalised (including mechanical ventilation and death), OR Non-hospitalised severe disease, defined as Non-ambulant for $\geq$ 3 consecutive days OR Unable to work for $\geq$ 3 consecutive  "pretty much confined to bed (meaning finding it very difficult to do any normal daily activities"  "I do not feel physically well enough to go to work" Secondary outcomes: All assessed at 6 and 12 months following randomisation unless otherwise indicated. The following outcomes are for both COVID-19 and fever or respiratory illness: presence of disease, days unable to work, days confined to bed, of days with symptoms, pneumonia, need for oxygen therapy, admission to critical care, need for mechanical ventilation Symptomatic or severe COVID-19, fever or respiratory illness Time to first symptom of COVID-19, fever or respiratory illness Deaths Number of days of unplanned absenteeism Type and severity of local and systemic adverse event over the 3 months following randomisation Planned exploratory analyses: episodes of and time to first recurrence of herpes simplex recurrence, immunological studies 7244 adult healthcare workers from Brazil, Europe and Australia TRIAL **POPULATION** (Victoria, Western Australia, South Australia and New South Wales) will be involved in the study, plus 2834 recruited in the earlier stage of this study. Key exclusion criteria are having BCG vaccine

contraindication, previously had a SARS-CoV-2 positive test result and prior involvement in this trial at an alternate study site. Participants will be randomised at 1:1 ratio giving approximately 5039 per group.

Multiple sites will enrol healthcare workers in Brazil, Europe and

Study Name: BCG vaccination to Reduce the impact of COVID-19 in healthcare workers (BRACE) trial RCH HREC number: 62586

Australia.

Version & date: version 12.0 dated 17May2022

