Further studies looking at BCG revaccination in individuals with positive TST or IGRA do not show increased risk of significant adverse effects. A case-control study of 200 healthy nursing students in India included 28 participants with a positive IGRA who received BCG revaccination. There were no serious side effects reported and no participants developed active tuberculosis during the follow-up study period. A randomised controlled trial of BCG revaccination in healthy adults with a positive TST (>15mm) with or without isoniazid pretreatment (n=82) showed no difference in the rate of reactions between groups with only local injection site reactions (35-76%) and mild systemic adverse effects (19%) including headache, fever and nausea. Among the 76% of participants who developed ulceration the median ulcer size was 5mm (IQR 4.0-6.0). Maximum ulcer diameter did not correlate with IGRA result prior to BCG vaccination in either group. There were no reports of regional lymphadenitis or serious morbidity.

Enhanced routine passive surveillance of BCG revaccinated school children in the BCG-REVAC trial in Brazil is available for 71718 individuals. There are only 33 reported adverse events of which 60% were local cutaneous reactions and 28% axillary lymphadenopathy without suppuration. There were no deaths, permanent injuries or disseminated infections reported. In a case series of 13 children who experienced adverse events following BCG revaccination in Brazil all developed local ulceration or abscess formation with complete recovery following antimycobacterial therapy. There were no cases of suppurative lymphadenitis or disseminated BCG. Further, an ongoing randomised trial in 150 participants in the US is giving repeat BCG (two vaccinations in the first year, then annually for 4 years) to adults aged 18-65 with type 1 diabetes to test if multiple BCG vaccinations can improve diabetic control and prevent complications. They have reported variable local reactions but no increased risk of lymphadenopathy or disseminated BCG ([name], personal communication).

The data presented above supports the WHO position that while BCG revaccination is not recommended due to a lack of evidence of efficacy against tuberculosis the risk of administering BCG vaccine to persons with positive tuberculin reactions due to either prior BCG vaccination or to natural infection is minimal.

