## Risks related to Placebo injection

Having an injection can sometimes cause very minor pain from the needle or be uncomfortable. The 0.9% NaCl is an inert salt solution that will not cause any degree of local reaction. The placebo injection will be administered by a trained immunization nurse.

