- o fever (using self-reported questionnaire), or
- at least one sign or symptom of respiratory disease including cough, sore throat, shortness of breath, respiratory distress/failure, or runny/blocked nose (in combination with another respiratory symptom or fever)

fever or respiratory illness, as defined above

- Severe fever or respiratory illness defined as:
  - o Death, OR
  - o Hospitalised, OR
  - o Non-hospitalised severe disease, defined as non-ambulant  $^1$  for  $\geq 3$  consecutive days or unable to work  $^2$  for  $\geq 3$  consecutive days

as a consequence of fever or respiratory illness, as defined above

-  "pretty much confined to bed (meaning finding it very difficult to do any normal daily activities"
-  "I do not feel physically well enough to go to work" (excludes stay at home exclusively for quarantine/workplace restrictions)
- Number of episodes of fever or respiratory illness, as defined above
- Number of days unable to work (using self-reported questionnaire) due to fever or respiratory illness, as defined above (excludes quarantine/workplace restrictions)

Study Name: BCG vaccination to Reduce the impact of COVID-19 in healthcare workers (BRACE) trial

RCH HREC number: 62586

Version & date: version 12.0 dated 17May2022

	Number of days confined to bed (using self-reported questionnaire) due to fever or respiratory illness, as defined above     Number of days with symptoms due to fever or respiratory illness
	
 
Pneumonia within a febrile or respiratory illness (using self-reported questionnaire and/or medical/hospital records)
 
Need for oxygen therapy for a febrile or respiratory
 

	illness (using self-reported questionnaire and/or hospitalisation records)  • Admission to critical care for a febrile or respiratory illness (using self-reported questionnaire and/or medical/hospital records)
	Need of mechanical ventilation for a febrile or respiratory illness (using self-reported questionnaire and/or medical/hospital records)      Deaths as a consequence of an episode of fever or
	respiratory illness  Duration of hospitalisation for a febrile or respiratory illness (using self-reported questionnaire and/or medical/hospital records)

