## 8.2 Capturing and eliciting adverse event information

For the period of randomisation to 3 months post randomisation only, the following are non-serious adverse events of interest for this study:

- At injection site:
  - o Reaction (pain, tenderness, redness, swelling) of grade 3 (severe) or 4 (potentially life threatening)
  - o Abscess
  - o Large ulcer (>1.5 cm diameter)
  - o Keloid scar
  - Unusual local reaction
- Lymphadenopathy (in region of injection site)
- BCG osteitis/osteomyelitis
- Disseminated BCG infection (BCG-osis)
- Allergic reaction due to IP
- Fainting episode, seizures and convulsions following IP administration (recorded on the day of IP administration only)

Only these non-serious AE and all SAE, occurring between randomisation and 3 months post randomisation, will be recorded for this study. If applicable, for the remainder of the follow-up period, sites may additionally document participants' AE as required to meet reporting requirements of the applicable HREC/s and/or regulatory authority.

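### Isolated fever just after the injection counts as illness under objective 7, so any reaction fever would bias that outcome, and the meta-analysis built on it, against BCG by an unknown amount

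*Protocol*

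**What the plan says.** **Illness definition.** Under objective 7 in Section 3.2, an episode is either "fever (using self-reported questionnaire), or" at least one respiratory sign or symptom. A runny or blocked nose counts only together with another symptom; fever needs no companion, test or attribution.

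**Time window.** "All the following measures will be assessed, over the 12 months following randomisation". No start delay is given. The schedule in Section 7.2 begins weekly surveys in week 1, and Section 7.3 has them ask about "Any symptoms of COVID-19: fever or at least one sign or symptom of respiratory disease".

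**Fever after BCG.** Section 2.3.1 (Trials of BCG revaccination) reports "mild systemic adverse effects (19%) including headache, fever and nausea" in a trial of 82 TST-positive adults. The list of expected, uncommon and rare BCG reactions in the same section does not name fever. On the control injection it says: "The 0.9% NaCl is an inert salt solution that will not cause any degree of local reaction".

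**Safety capture.** Section 8.2 gives a fixed list of non-serious events and states: "Only these non-serious AE and all SAE, occurring between randomisation and 3 months post randomisation, will be recorded for this study". Fever is not listed. The two-week diary is introduced as "For local reaction to injection: the Vaccine Diary (daily diary for the two weeks following injection", and the toxicity scale in Section 8.5 grades local items only. The synopsis nevertheless names as an outcome "Type and severity of local and systemic adverse event over the 3 months following randomisation".

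**Role of the outcome.** Objective 7 is secondary in Stage 2. Section 11.1 makes febrile or respiratory illness over 12 months the main objective of the revised Stage 1 plus Stage 2 meta-analysis.

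**The concern.** Take a BCG recipient with a non-serious fever on day 2, no respiratory symptom and no positive SARS-CoV-2 test. Under Section 3.2 this is an illness episode. Under Section 8.2 it is not a recordable adverse event. If the injection caused the fever, a reaction to BCG has been scored as a failure of BCG to prevent illness.

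The scoring rule is the same in both arms and background fevers count in both. A BCG reaction, however, can arise only where BCG was given. The excess would therefore fall on the BCG arm and enter illness incidence, episode counts, symptom days and bed days. Time to first illness, listed in the synopsis, is the most exposed because the extra events would come at the very start of follow-up.

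The population makes this more than theoretical. Revaccination is allowed, TST screening is deliberately omitted, and Section 2.3.1 says newborn BCG has been mandatory in Brazil since 1976. Some participants will resemble those in the cited revaccination trial.

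**Working it through.** **The plan's own figures.** The protocol gives no event rate, effect size or power for objective 7, so there is nothing to reproduce for this outcome. The sample size used as background does reproduce: for severe COVID-19 (4% against 4% × 0.667, alpha 0.04, 80% power) the two-proportion formula gives 6090 in total against the stated 6076, and 3038 per group gives 79.9% power.

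**Inputs**
- From the protocol: 3622 per arm; 3038 per group in the severe COVID-19 calculation; 16% loss to follow-up, so 3622 × 0.84 = 3042 per arm.
- Assumed: *f*, the share of BCG recipients with a reaction fever, 1-5%. The cited 19% pools headache, fever and nausea, and the fever share is not given.
- Assumed: *p*, the 12-month risk of febrile or respiratory illness in controls, 40-70%.
- Assumed: two-sided alpha 0.05, and reaction fever independent of other illness.

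**Step 1: inflation of the BCG proportion when BCG has no true effect.** A reaction fever adds a new case only among those who would otherwise have had no illness, so inflation = *f* × (1 − *p*).

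| *f* | Extra episodes (3622 × *f*) | *p* = 40% | *p* = 60% | *p* = 70% |
|---|---|---|---|---|
| 1% | 36 | 0.6 points | 0.4 | 0.3 |
| 2% | 72 | 1.2 | 0.8 | 0.6 |
| 5% | 181 | 3.0 | 2.0 | 1.5 |

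**Step 2: difference detectable with 80% power, 3038 per group.** (1.96 + 0.84) × √(2*p*(1 − *p*)/3038).
- *p* = 40% or 60%: 2.80 × √(0.48/3038) = 2.80 × 0.01257 = 3.5 points.
- *p* = 70%: 2.80 × √(0.42/3038) = 2.80 × 0.01176 = 3.3 points.

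At *p* = 60% the inflation is 0.4/3.5 = 11% to 2.0/3.5 = 57% of a detectable difference. Over the whole assumed range it is 0.3/3.3 = 9% to 3.0/3.5 = 86%.

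**Step 3: effect on a true benefit.** Observed BCG risk = 1 − (1 − *p* × RR)(1 − *f*), with 3042 per arm. Take a true RR of 0.90.
- *p* = 50%: observed RR 0.911, 0.922 and 0.955 at *f* = 1%, 2% and 5%. Power falls from 97% to 94%, 86% and 42%.
- *p* = 30%, below the range used above: power falls from 74% to 50%, 26% and under 1%.
- *p* = 70%: power stays at 99% or more throughout.

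**Step 4: no true effect, *f* = 5%.** The chance of a significant result against BCG is 84%, 50% and 25% at *p* = 30%, 50% and 70%.

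The result is driven by *f* and *p*, and the protocol fixes neither.

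**The case against.** **The premise is thin.** Fever after BCG rests on one trial of 82 adults selected for a large TST response, and the protocol's own reaction list omits it. This stands. A reader might take 19% as the fever rate, but that figure covers three symptoms together. At *f* = 1% the effect is small.

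**Systemic safety data are not absent.** A reader might infer from the closed list that the systemic part of the safety outcome has no data. Section 8.2 does not support that: it lists disseminated BCG infection, osteitis or osteomyelitis, allergic reaction, and fainting or seizures, and all SAEs are recorded for three months. Only ordinary non-serious systemic reactions such as fever are missing.

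**The information is already collected.** Section 7.3 records symptoms for each illness episode, including fever, headache and nausea, with onset and cessation dates. This also stands, and it makes the fix cheap.

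**Absenteeism should keep reaction days.** A working day lost to a vaccine reaction is a real cost of vaccinating staff, and the rationale in Section 2 is workforce availability. Taking such days out of objective 8 would favour BCG. I agree that objective 8 should stay as it is.

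**This is SAP detail.** An onset window is often left to the SAP, and Section 11.3 defers variable details there. The point does not rest on silence, however. Section 3.2 states a definition that counts these fevers, and the synopsis and Section 8.2 differ on what is recorded.

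**Conclusion.** The point holds as a cheap improvement to a stated outcome definition. As written, objective 7 scores any reaction fever as illness, and the resulting bias runs against BCG. It could hide a benefit or suggest harm; it could not create a false benefit.

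The size cannot be settled from the protocol. With 1-5% reaction fever and 40-70% background risk it is 0.3-3.0 points against about 3.5 detectable, which runs from negligible to material.

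Two further inferences are not supported. The first is that the primary outcomes are compromised: both also require a positive SARS-CoV-2 test, so an isolated reaction fever does not meet them. The second is that the scoring differs by arm: the rule is identical, and only the source of the excess differs. In Stage 1 both arms also received influenza vaccine at randomisation, so early fever there need not come from BCG.

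**What to change.** 1. In Section 3.2 (objective 7) and in the Section 11.1 meta-analysis, add a pre-specified analysis, identical in both arms. It does not count an episode of fever with no respiratory symptom and no positive SARS-CoV-2 test whose onset is within 14 days of the injection. Stage 1 controls had no trial injection, so their window should run from randomisation. Report this analysis beside the count from day 0.
2. Tabulate these early isolated fevers by arm under objective 9.
3. Reconcile the synopsis with Section 8.2, so that the systemic events promised match those recorded.
4. Leave objective 8 unchanged and add no diary items. Section 1.3 expected injections to finish by March 2021 and this version is dated May 2022, so on that timetable nobody could still complete a two-week diary.

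The rule should be fixed before allocation is revealed (Section 6.1). The cost is one sentence, one additional analysis and one table from data already held. The downside is that a few genuine fever-only infections in the first 14 days are left out of that analysis, in both arms.
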